6.5 Treatment

7. Efficacy Assessments

60 (93)

8. Safety Assessments

8.1 Assessment of AEs by direct question to subject and evaluation of subject

Safety evaluations for this study include an interview of the subjects at each visit to obtain information about any medical occurrence that meets the definition of an AE. Each subject should be questioned about AEs at each study visit following the screening visit. The question asked should be asked: "Since your last clinical visit have you had any health problems?" Information on AEs can also be obtained from signs and symptoms detected during each examination by the Investigator or designee, which should include visual inspection of the treatment area.

AEs must be documented in the source document and eCRF without regard for cause or relation to investigational product. If in the process of the interview, additional information regarding medical history or pre-planned medical or surgical procedures is revealed, it must be documented in the source document(s) and eCRF.

It is the responsibility of the Investigator to determine severity of the AE and relatedness of the event to the study product.

[REDACTED]

[REDACTED]

[REDACTED]

8.5 Laboratory assessments

Pregnancy Test

For all women of childbearing potential, including those currently using contraception, a urine pregnancy test is required prior to receiving any study treatment (Day 1, touch-up, or re-treatment). **The test result must be negative for the subject to receive any treatment with study product.** The test result will be documented in the subject's file and eCRF.

8.6 Adverse events

8.6.1 Definition of an adverse event

An AE is any untoward medical occurrence, unintended disease or injury, or untoward clinical signs (including abnormal laboratory findings) in subjects, users or other persons⁶, whether or not related to the study product.

This definition includes:

- a) events related to the investigational product or the reference product
- b) events related to the procedures involved

8.6.2 Definition of a serious adverse event

A serious adverse event (SAE) is an AE that:

- a) led to death,
- b) led to serious deterioration in the health of the subject, that either resulted in
 1. a life-threatening⁷ illness or injury, or
 2. a permanent impairment of a body structure or body function, or

⁶ For users or other persons, this definition is restricted to events related to the investigational product.

⁷ The term "life-threatening" in the definition of "serious" refers to an event in which the patient was at risk of death at the time of the event; it does not refer to an event which hypothetically might have caused death if it were more severe. (Source: ICH-E2A clinical safety data management: definitions and standards for expedited reporting).

3. in-patient or prolonged hospitalisation⁸, or
4. medical or surgical intervention to prevent life-threatening illness or injury or permanent impairment to a body structure or a body function,

c) led to foetal distress, foetal death, or a congenital abnormality or birth defect

An AE does not need to be recorded as a SAE if it only represents a relapse or an expected change or progression of the condition that was the cause of the study treatment, without the development of new symptoms and signs.

In cases of doubt, whether an AE fulfils a serious criterion or not, there should be a predisposition to report as a SAE rather than not report as such (see section 8.5.5).

8.6.3 Recording instructions

AEs will be recorded once a subject is enrolled (i.e., randomized and/or treated) in the study. All other events that occur after the subject signs the ICF but before enrollment will be recorded in the subject's medical history. Each AE should be fully recorded in the subject's source document and the eCRF. Beginning after initial treatment on Day 1, each subject should be questioned about AEs at each study visit. The question asked should be: "Have you had any health problems since receiving study treatment?" Information on AEs can also be obtained from signs and symptoms detected during each examination.

When an AE is related to a device deficiency including technical device malfunction, the AE should be recorded in the AE eCRF and the technical complaint should be reported separately on the study complaint form.

Investigators, or other study site personnel, shall record all AEs in the eCRF, including:

- a) Event term (recorded in standard medical terminology and avoiding abbreviations)
- b) Description of event and affected area
- c) Start date (first day with symptoms)
- d) Stop date (last day with symptoms)
- e) Intensity (mild, moderate, or severe according to definition in Section 8.6.3.1)
- f) Seriousness (serious or not serious, according to definition in Section 8.6.3.2)
- g) Causal relationship to study product or study product injection procedure (yes or no)
- h) Action taken (none, medication treatment, non-medication treatment, or other procedures/tests, subject withdrawn)
- i) Outcome of the AE (ongoing, recovered, recovered with sequelae, death, chronic/stable, not recovered at the end of the study)

The pre-defined, expected post-treatment events shall be assessed separately. These events shall be collected daily by subjects in a Diary for up to 28 days after each treatment.

⁸ Planned hospitalisation for a pre-existing condition, or a procedure required by the CSP, without serious deterioration in health, is not considered a SAE. (Source: ISO14155:2011).

8.6.3.1 *Intensity*

Intensity will be recorded for each reported AE. The following definitions of intensity are to be used:

Mild: Awareness of symptoms or signs, but easily tolerated (acceptable)

Moderate: Enough discomfort to interfere with usual activity (disturbing)

Severe: Incapacity to work or to do usual activity (unacceptable)

If the intensity changes within one day, the maximum intensity of the AE during that day shall be recorded.

8.6.3.2 *Causal relationship and seriousness*

Each AE, serious as well as non-serious, shall be assessed by the Investigator for causal relationship with the study product and its use (the injection procedure) and for seriousness (Yes or No) of the event.

A two-point scale (Yes or No response) shall be used for the causality assessments. The Investigators shall be asked to indicate a response to each of the following questions in the eCRF:

- “Do you consider that there is a reasonable possibility that the event may have been caused by the study product?”, and
- “Do you consider that there is a reasonable possibility that the event may have been caused by the device injection procedure?”

If any of these questions is answered ‘Yes’, the AE is considered related.

Each AE will also be assessed for causal relationship and seriousness by the Sponsor, in order to fulfil regulatory requirements.

8.6.4 *Reporting of adverse events*

Adverse event reporting on each subject shall start upon enrollment (i.e., randomized and/or treated with study product) in the study. Any events that occur after the subject signs the ICF but before enrollment will be recorded in the subject’s medical history. The reporting shall continue during each follow-up visit (including telephone contacts and unscheduled visits) until the last scheduled visit in the study.

All AEs, non-serious as well as serious, are to be reported as an AE in the eCRF.

8.6.5 *Reporting of adverse events of special interest (AESIs)*

AESIs should be reported (using the AE Clarification Form) within 24 hours of awareness to the Sponsor/CRO at the email address [REDACTED]. In case of difficulty to obtain all the required information within 24 hours, an initial report can be submitted with follow up information provided within 24 hours of awareness of the new information.

The following information should be provided when reporting an AESI:

- Subject identification (subject number and initials)
- Event description including observed symptoms

- Medical history related to event
- Event onset date and time
- Depth of injections
- Interventions implemented to treat event
- Event outcome (with resolution date and time if applicable)
- Relatedness to study product or procedure
- Seriousness of event
- Study treatment information (number of injections, date of injections, name of product injected, volume injected, etc.)

If the Investigator assesses an AESI to be serious, an SAE report should be submitted as specified in section 8.6.6.

Upon receipt of the AESI report, the Medical Monitor and Sponsor will review the information provided, assess the event, and report to the IRB and RA as applicable.

8.6.6 Reporting of serious adverse events

The Investigator shall report any **SAE** to the Sponsor **immediately but not later than 24 hours of awareness of the event**. This initial report can be made via e-mail.

Follow-up information and data missing in the initial SAE reporting shall be gathered as soon as possible and reported immediately but not later than 24 hours of awareness of the new data. Complete and adequate information on each SAE is required. All attempts to obtain this information, including dates for follow-up activities, must be documented by the Investigator or designated study staff.

Supporting documentation to be provided with the SAE report:

- Concomitant medication form
- Concomitant procedure/treatment form
- AE form
- Medical history form

- Any other relevant supporting documentation (e.g. hospital notes, death certificate, autopsy reports etc.)

Safety E-mail for reporting: [REDACTED]

The SAE form must be signed and dated by the Investigator. If the initial 24-hour SAE report does not contain full information or if it is made without using the SAE form the fully completed and signed SAE form shall be e-mailed to the safety email address. A copy of the fully completed SAE form shall be kept at the site.

In addition, the Investigator shall report SAEs to the responsible IRB without undue delay, if applicable according to national or local regulations. The Investigator is responsible for checking what reporting procedures are applicable for his/her IRB regarding SAEs and final report of the outcome of the study and to comply with such reporting procedures during the study period.

[REDACTED]

[REDACTED]

[REDACTED]

[REDACTED]

[REDACTED]

[REDACTED]

[REDACTED]

[REDACTED]

[REDACTED]

8.6.9 Pregnancy

Pregnancy itself is not regarded as an AE.

If there is a pregnancy after the subject has been treated, the subject must continue to be followed and the outcome of pregnancy must be reported even if the delivery occurs after study completion. Additional treatment with study product is not allowed once a pregnancy is noted.

A pregnancy confirmed during the study period after treatment must be reported by the Investigator on a pregnancy report form immediately upon acknowledgement and submitted to the Sponsor/CRO Safety email specified in section 8.6.5. The report can be prospective or retrospective. Follow-up shall be conducted to obtain outcome information on all prospective reports.

Cases that led to foetal distress, foetal death, or a congenital abnormality or birth defect are to be regarded as SAEs and shall be reported on the exposure *in utero* report form to the Sponsor immediately but no later than 24 hours after the Investigator's awareness. These events shall be handled as SAEs during data processing. Other complications during the pregnancy that are related to the pregnant woman and fulfils any serious criteria, such as pre-eclampsia requiring hospitalization, shall be reported and handled as SAEs. Elective abortions without complications shall not be reported as AEs.

8.6.10 Anticipated adverse events

Information regarding anticipated AEs for the investigational product is included in the study-specific Instructions for Use. For information regarding anticipated AEs for Juvéderm Voluma® XC (reference therapy) please refer to the manufacturer's website (See Section 2.3.1).

8.7 Device deficiencies

8.7.1 Definition of a device deficiency

A device deficiency is defined as an inadequacy of a medical device with respect to its identity, quality, durability, reliability, safety⁹, or performance.

Note: Device deficiencies include malfunctions, use errors, and inadequate labelling.

8.7.2 Recording instructions

When a device deficiency is discovered, Part A of the clinical study complaint form shall be completed by the Investigator or qualified designee and entered into the eCRF. The type of complaint shall be described and injury to the subject or user or unintended exposure to study product shall be reported as applicable. If an injury has occurred, an AE or an SAE form shall be completed as applicable (refer to section 8.6.5). If no SAE was experienced as a result of the device deficiency, the Investigator shall assess whether or not the device deficiency could have led to an SAE if:

- Suitable action had not been taken,
- Intervention had not been made or,
- Circumstances had been less fortunate

In Part B of the clinical study complaint form, the Sponsor will make the same assessment.

⁹ Inadequacy of device safety refers to properties of the device which could have or have led to an AE.

8.7.3 Reporting of device deficiencies

A device deficiency that led to a SAE and any device deficiency that could have led to a SAE shall be reported within 24 hours after the Investigator's awareness in accordance to section 8.6.5

In order to fulfil regulatory reporting requirements, all deficiencies with the study product must be assessed by both the Investigator and the Sponsor to determine if it could have led to a SAE.

If a SAE has resulted from a device deficiency or if either the Investigator or the Sponsor assesses that the device deficiency could have led to a SAE the Sponsor is responsible for reporting the device deficiency to RA and the PI is responsible for reporting it to the IRB.

The deficient study product shall be kept by the study site until the Sponsor QA complaints group has confirmed whether the product shall be returned to Sponsor for further study or if it can be destroyed.

9. Data Handling and Management

9.1 Data management

Data management based on GCP refers to the activities defined to achieve safe routines to enter clinical data information into a database, efficiently and avoiding errors. The data management routine includes procedures for handling eCRFs, database set-up and management, data entry and verification, data validation, and documentation of the performed activities including information of discrepancies in the process. The data management process will be described in detail in the data management plan (DMP).

The database, the data entry screens and program will be designed in accordance with the CIP and the eCRF. Data validation will be performed by computerised logical checks and manual review. Drugs and events will be coded in accordance with World Health Organization (WHO) Drug and medical dictionary for regulatory activities (MedDRA) dictionaries as specified in the DMP. SAEs in the clinical database will be reconciled against the data in the safety database.

When all efforts have been made to ensure that the data recorded in the eCRFs and entered in the database is as correct and complete as possible, the clinical database will be locked. Study data will be transferred to SAS datasets which thereafter will be write-protected. Statistical analyses will be generated in SAS using data from the locked datasets.

9.2 Electronic case report forms

A 21 Code of Federal Regulations (CFR) Part 11-compliant electronic data capture application will be used to collect, modify, maintain, archive, retrieve, and transmit study data. An eCRF is required and shall be completed electronically for each screen failure as well as enrolled subjects.

The eCRF includes password protection and internal quality checks, such as automatic range checks, to identify data that appear inconsistent, incomplete, or inaccurate. Study data shall be entered directly from the source documents, which are to be defined at each site before inclusion of the first subject.

Authorized study site personnel designated by the Investigator shall complete data collection. Appropriate training and security measures shall be completed with all authorized investigation site personnel prior to the study being initiated and any data being entered into the system for any subject.

The study data is the sole property of the Sponsor and shall not be made available in any form to third parties, except for authorized representatives of appropriate RA, without written permission from the Sponsor. At the end of the study, electronic data are kept at the Sponsor and a copy (provided by the vendor) at the study site as part of the Investigator file.

Any delegation of collection of data shall be specified in a signature and delegation log.

9.2.1 Data entry

All data shall be entered in English. The eCRFs should always reflect the latest observations on the subjects participating in the study. Therefore, every effort should be made to complete the eCRFs within a reasonable time frame (for example, 3-5 working days) after the subject's visit. The subject's identity must always remain confidential, i.e. the name and address of the subjects must not be registered in the eCRFs or in the database. The Investigator must verify that all data entries in the eCRFs are accurate and correct. If some assessments are not done, or if certain information is not available, not applicable or unknown, the Investigator shall indicate this in the eCRF. The Investigator shall electronically sign off on the study data. By signing, the Investigator takes responsibility for the accuracy, completeness, and legibility of the data reported to the Sponsor in the eCRF.

9.2.2 The query process

The monitor shall review the eCRFs and evaluate them for completeness and consistency. Each eCRF shall be compared with the respective source documents to ensure that there are no discrepancies between critical data. All entries, corrections, and alterations shall be made by the PI or his/her authorised designee. The monitor cannot enter data in the eCRFs. Once study data have been submitted to the central server via the eCRF, corrections to the data fields will be audit trailed, meaning that the reason for change, the name of the person who made the change, together with time and date will be logged. Roles and rights of the site personnel responsible for entering study data into the eCRF shall be determined in advance. If discrepant data is detected during review of the data, either by the Sponsor or its representatives, the responsible data manager or monitor shall raise a query in the electronic data capture application. The query shall state the question or data to be changed and shall be resolved in the system by the PI or his/her authorised designee. The appropriate study site personnel shall answer the queries in the eCRF within a reasonable timeframe (for example, 3 working days). Answered queries will be audit trailed by the electronic data capture application meaning that the name of study site personnel, time, and date is logged. Answered queries will then be closed by the appropriate study personnel (*i.e.*, data manager, site monitor, etc.).

9.2.3 User identification

Electronic CRFs will be automatically appended with the identification of the creator, by means of their unique User ID. Specified records shall be electronically signed by the Investigator to document his/her review of the data and acknowledgement that the data are accurate. This will be facilitated by means of the Investigator's unique User ID and password; date and time stamps will be added automatically at time of electronic signature. If an entry in an eCRF

requires change, the correction shall be made in accordance with the relevant software procedures.

9.2.4 Audit trail

All changes will be fully recorded in a protected audit trail and a reason for the change shall be stated. Once all data have been entered, verified, and validated, the database will be locked.

9.3 Source documents

Source documents are all documents used by the Investigator or hospital that relate to the subject's medical history, that verifies the existence of the subject, the inclusion and exclusion criteria, and all records covering the subject's participation in the study. They include laboratory notes, memoranda, material dispensing records, subject files, etc.

The Investigator is responsible for maintaining source documents. These shall be made available for inspection by the monitor at each monitoring visit. The Investigator must submit a completed eCRF for each subject for whom signed informed consent has been collected. All supportive documentation submitted with the eCRF, such as laboratory or hospital records, shall be clearly identified with the CTN and subject number. Any personal information, including name, shall be removed or rendered illegible to preserve individual confidentiality.

9.4 Record keeping and access to source data

The Investigator/Institution shall permit study-related monitoring, audits, IRB review, and RA inspections and shall provide direct access to the source data/medical record including the identity of all participating subjects (sufficient information to link records, i.e. eCRF, medical records, original signed informed consent forms and detailed records of study product accountability). The records shall be retained by the Investigator as required by local legislation and international guidelines. Any transfer of responsibility for storage of the records shall be documented and the Sponsor shall be informed in writing.

The Sponsor shall verify that each subject has consented in writing to direct access to the original medical record/source data (by the use of written subject information and signed informed consent). The data recorded in the eCRFs will be checked for consistency with the source documents/medical record by the monitor during monitoring (source data verification; SDV). In order to be able to perform SDV, information about each subject's participation in the study has to be detailed in the medical record.

9.5 Document and data retention

All records pertaining to the conduct of the study, including signed eCRFs, informed consent forms, study product accountability records, source documents, and other study documentation must be retained for as long as is specified in the CTA. Measures shall be taken to prevent accidental or premature destruction of these documents (e.g. protection against damage and unauthorized access, preferably by storage in a fire-proof cabinet).

It is the Investigator's responsibility to inform the Sponsor in writing if the Investigator file is moved or if the responsibility for the documents is transferred to someone else.

10. Statistical Methods

10.3 Demographics, baseline assessments, and subject characteristics

Demographic endpoints, baseline assessments, and subject characteristics will be presented based on the ITT analysis set using descriptive statistics by treatment, as appropriate.

10.4 Efficacy analysis

10.5 Safety analysis

[figure not shown]
Number and percentage of subjects reporting diary events, as collected in the [REDACTED] diary, will be presented by treatment, type of event and maximum intensity. Number of days with the event will be summarized by treatment [REDACTED]

10.6 Handling of missing data

Number of missing values will be summarized and reported as appropriate.

Missing data for the primary analysis [REDACTED] will be handled using the hot deck imputation method.

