### 3.3 Treatments and Assignment to Treatments

Subjects will be enrolled in two groups – Group A and Group B.

**Group A:** Approximately 210 subjects, over the age of 21, will be randomized in a 2:1 ratio, to receive treatment with either GAL1704 or Juvéderm Voluma® XC, respectively. Approximately 140 subjects will be treated with GAL1704 and 70 subjects will be treated with Juvéderm Voluma® XC.

[REDACTED]  
sites will have a BE, blinded to the treatment provided to each subject, who will perform the blinded assessments.

**Group B:** An additional 60 subjects will be enrolled and treated with GAL1704 only. These subjects will be treated using a split face design, i.e., one cheek will be treated using a small blunt tip cannula and the other cheek will be treated using the co-packed needle.

[REDACTED]  
[REDACTED] The Treating Investigator will not be blinded to study treatments and will administer the treatments to each subject. Safety assessments will be performed by non-blinded personnel.

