### 3.4 Determination of Sample Size

For sample size calculation of Group A,

Accounting for approximately 12% drop-outs and non-evaluable subjects due to protocol deviations at Week 12, a total of approximately 210 subjects will be randomized in the study. It is expected that the number of randomized subjects will be similar across the study sites.

For sample size calculation of Group B, [REDACTED]

Accounting for approximately 10% drop-outs, 60 subjects will be needed.

Thus, a total of 270 subjects will be included in the study.

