## 4.0 GENERAL ANALYSIS CONVENTION

Data collected in this study will be documented using summary tables and subject data listings. Continuous endpoints will be summarized using descriptive statistics, e.g. number of subjects, mean, median, standard deviation, minimum and maximum values. Categorical endpoints will be presented in frequency tables with number and percentage of observations for each level.

Group A and Group B will be analyzed and presented separately. Data will be summarized by treatment group in Group A and by injection tool (Needle/Cannula) in Group B.

Confidence intervals will be two-sided and constructed at a confidence level of 95%.

Study days will be calculated relative to the date of first dose of study product. Day 1 will be the first day of study product administration in the study. The day prior to Day 1 will be Day -1. There will be no Day 0.

Baseline will be the last assessment prior to the first dose of study product.

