### 10.1 Primary Effectiveness Analysis

[REDACTED]

[REDACTED]

[REDACTED]

Primary effectiveness analysis (Group A only)

[REDACTED]

[figure not shown]
- a) Non-inferiority will be established if the upper limit of the CI is below the non-inferiority margin of 0.5 units.
- b) Superiority will be declared if the upper limit is below 0.

This decision criteria is consistent with a gate-keeping strategy (testing for superiority following the test for non-inferiority) to maintain the overall type I error rate at 2.5%.

Group B effectiveness success criterion

The CI will be used for assessing non-inferiority in the following way. Non-inferiority will be established if the upper limit of the CI is below the non-inferiority margin of 0.5 units.

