## 11.0 STATISTICAL/ANALYTICAL ISSUES

### 11.1 Handling of Dropouts or Missing Data

Number of missing values will be summarized and reported as appropriate.

[REDACTED]

Impact of missing data on the primary analysis for Week 12 endpoints will be evaluated by performing sensitivity analysis based on the observed cases in the ITT population.

[REDACTED]

All other effectiveness endpoints will be evaluated based on the observed cases in ITT, i.e. no imputations will be done.

If the adverse event start date is missing, it will be assumed that the AE started on the day of the most recent treatment. Missing stop date for adverse event will not be imputed.

If the adverse event severity assessment is missing, the highest level of severity will be assumed. Missing relationships in adverse event will be imputed as related. AEs will be considered as serious if the assessment on whether the AE is serious or not is missing.

The observed cases in the Safety population will be used for all other safety analysis.

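### Does hot deck imputation of missing Week 12 scores make the primary confidence interval too narrow to hold the 2.5% type I error?

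*Protocol*

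**What the plan says.** Protocol 10.6 gives the only visible statement on imputing the primary endpoint: missing data "will be handled using the hot deck imputation method". Part of that sentence, before the verb, is redacted.

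The decision rests on a confidence interval. SAP 4.0 states: "Confidence intervals will be two-sided and constructed at a confidence level of 95" percent. SAP 10.1 adds: "Non-inferiority will be established if the upper limit of the CI is below the non-inferiority margin of 0.5 units". Superiority follows if the upper limit is below 0. SAP 10.1 presents this sequence as a gate-keeping strategy "to maintain the overall type I error rate at 2.5" percent. Under SAP 5.0, effectiveness is analysed in all randomized subjects, so imputed scores would enter the interval.

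Some missing scores are expected. The Group A sample size in SAP 3.4 is set "Accounting for approximately 12% drop-outs and non-evaluable subjects due to protocol deviations at Week 12". SAP 11.1 plans a "sensitivity analysis based on the observed cases in the ITT population" to assess the effect of missing data at Week 12, and SAP 5.0 and 10.0 repeat the primary analysis in the per-protocol population. The visible part of SAP 11.1 does not mention hot deck; there are redacted blocks directly before and after its sensitivity sentence.

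**The concern.** Hot deck fills a gap with a score borrowed from an observed subject. Done once and then treated as real data, it goes wrong in two ways. The copied scores carry no new information, yet the standard error shrinks as if they did. The random choice of donor also adds noise that the standard error ignores. Both make the interval too narrow, and a narrow interval makes non-inferiority and superiority easier to claim. If donors could come from the other arm, the difference would also be pulled toward zero, which again favours non-inferiority.

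A reader who sees hot deck named, with no mention of repeated draws, combining rules or a variance correction, may reasonably suspect this version. At stake would be the 2.5% error rate behind the trial's main claim.

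**Working it through.** **Inputs.** Two-sided 95% interval (SAP 4.0); margin 0.5 and overall error 2.5% (SAP 10.1); Group A allocation: "Approximately 140 subjects will be treated with GAL1704 and 70 subjects will be treated with Juvéderm Voluma® XC" (SAP 3.3); 12% planning loss (SAP 3.4). The standard deviation is not visible, so values from 0.6 to 1.0 are assumed.

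**The plan's own figure.** The upper limit of a two-sided 95% interval gives one-sided error 1 − Φ(1.96) = 0.025. This agrees with the stated 2.5%.

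**If the hot deck were single, within arm, with no variance correction.** Take n subjects in an arm, of whom r = n(1 − m) are observed, with scores missing completely at random.

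- Actual variance of the filled-in mean: s²/r + s²(n − r)/n².
- Variance the standard formula would report: about s²/n.
- Ratio: 1/(1 − m) + m. It is the same in both arms, so it also applies to the difference.
- One-sided error: 1 − Φ(1.96/√ratio).

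At m = 0.12 the ratio is 1/0.88 + 0.12 = 1.256 and its square root is 1.121. Then 1.96/1.121 = 1.749, and the error is 0.040.

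| Missing | Variance ratio | True SE / reported SE | One-sided error | Coverage |
|---|---|---|---|---|
| 3% | 1.061 | 1.03 | 2.9% | 94.3% |
| 5% | 1.103 | 1.05 | 3.1% | 93.8% |
| 8% | 1.167 | 1.08 | 3.5% | 93.0% |
| 12% | 1.256 | 1.12 | 4.0% | 92.0% |

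Simulation with 140 and 70 subjects, normal scores and a true difference equal to the margin gave 3.1% at 5% missing (SD 0.8) and 4.0% to 4.2% at 12% (SD 0.6 to 1.0).

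**If the hot deck were repeated.** An approximate Bayesian bootstrap hot deck within arm, with 20 imputations combined by Rubin's rules, gave 2.4% at 5% missing and 2.6% at 12% (12,000 simulated trials each, SD 0.8). The simulation error is about √(0.025 × 0.975/12,000) = 0.14 percentage points, so both agree with 2.5%. The observed-cases analysis gave 2.4% at both levels.

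**Which of the two do the documents describe?** Both are hot deck imputation methods, and Protocol 10.6 fits either. The text that could decide between them is not visible:

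- The Protocol 10.6 sentence is partly redacted.
- SAP 11.1, where the SAP's own imputation rule would be expected, is redacted on both sides of the sensitivity sentence.
- The model and interval construction in SAP 10.1 are largely redacted, and Protocol 10.4 shows no text on the primary analysis.
- SAP 2.0 defines baseline observation carried forward, a term used nowhere in the visible text. This suggests that the hidden text says more about missing data.
- The SAP contents list a section 18.0 on changes from the protocol, and its content is not visible. It therefore cannot be confirmed that the SAP keeps the protocol's method unchanged.

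**Donors from the other arm.** Nothing visible says or implies this. If it is assumed, simulated error at 12% missing is 6.0% at SD 1.0, 7.3% at SD 0.8 and 10.2% at SD 0.6. These figures describe the assumption and are not evidence about the plan.

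**The case for a change.** The strongest case for the concern is that the method clause in Protocol 10.6 is intact. The redaction comes before the verb, where it most naturally narrows which data are meant, and the clause then ends without a word on repetition or variance. A method that is named but left open allows a version that inflates error, always in the direction of an easier claim. The supporting analyses do not repair this: observed cases is a sensitivity analysis, the per-protocol repeat is supportive, and no visible rule says what follows if they disagree with the primary result.

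Much of this stands. The arithmetic for a single, uncorrected hot deck is right and hardly depends on the unknown standard deviation. Sensitivity analyses cannot restore the error rate of a primary interval.

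It does not show that the plan uses that version. A one-sentence summary in the protocol need not give the number of imputations, and the SAP sections that would give it are blacked out. The size is also an upper figure. The 12% in SAP 3.4 includes subjects lost to evaluation through protocol deviations, some of whom may still have a Week 12 score. Protocol 5.5 seeks an early termination visit to record the primary outcome where possible, and SAP 4.2 keeps out-of-window assessments. Both may reduce missing scores. The two planned supporting analyses should involve few or no copied scores, so a result that depends on imputation would be likely to show.

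**Conclusion.** The concern does not hold. It needs a single fill-in with an uncorrected variance, and the visible documents state neither. The only words that bear on the method are equally true of a repeated hot deck, which held 2.4% to 2.6% in simulation. To infer the faulty version from silence would charge redactions to the plan.

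The size is conditional: about 3.1% to 4.0% one-sided error for 5% to 12% missing if the hot deck is single, within arm and uncorrected, and no inflation if it is repeated and properly combined. These figures assume scores missing completely at random; the simulations also assume normal scores and an SD between 0.6 and 1.0. A reader with unredacted copies can settle the matter by looking up the number of imputations, the donor classes and the variance method in SAP 10.1 and 11.1.
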